3 DESCRIPTION OF DEVICES

3.1 Overview and hardware

The interoperable Artificial Pancreas System (iAPS) is an artificial pancreas system (as described in MAF-1625, Amendment #10), comprised primarily of an insulin pump, a continuous glucose monitor (CGM), and a cellular phone device to connect the components. The portable AP device is intended to adjust insulin doses when glucose concentration is, or is predicted to be, outside the

[figure not shown]
specified target range of 80-100 mg/dL. It includes a redundant safety control that will send warnings of impending hypoglycemia and recommend ingesting carbohydrates immediately to prevent hypoglycemia (Health Monitoring System).

The interoperable Artificial Pancreas System (iAPS) used in this study is described in MAF-1625, Amendment #10, and includes:

- A cellular phone device to connect to the insulin pump and CGM transmitter (Google Pixel 1, 2 or 3/3a)
- Dexcom G6 Sensor & Transmitter (G160069)
- Tandem t:AP insulin pump (San Diego, CA) (MAF-2032-A003)
- The same control algorithm successfully used with iAPS in G180011/002 and G200047 (Zone MPC with HMS), with modifications to the tighter target glucose range as recommended for pregnant women with diabetes to achieve increased time in range 63-140 mg/dL, and reduce postprandial hyperglycemia.
- The same Health Monitoring System (HMS) algorithm used in G180011/002 and G200047, which issues safety notifications to the subject and support personnel to prevent impending hypoglycemia, with minor modifications to the algorithm as noted above.

A schematic of the iAPS system being used in the study is shown in Figure 4.

Figure 4: Schematic of the representative principal system hardware components. The iAPS works with both Dexcom G5/G6 and with OmniPod and Tandem t:AP pumps. In this study we will only be using Dexcom G6 and Tandem pumps.

Letters of authorization for all devices used as part of iAPS system are included in MAF-1625, Amendment #10.

A. Dexcom G6 (Study CGM)

The AP System will be integrated with the Dexcom G6 (study CGM). The G6 transmitter sends data points directly to iAPS.

B. Tandem t:AP Pump

The Tandem t:AP insulin pump is a modified version of the Tandem t-slim insulin pump that is modified to work with an AP controller. It otherwise functions identically to the commercially available product. No other pumps will be used in this study.

C. Study Glucometer and Ketone Meter

Subjects will use the Contour NEXT blood glucose monitoring system (K150942 - Ascensia Diabetes Care US, Inc., [name]) to measure capillary blood glucose for CGM calibration and confirmation of CGM readings.

Subjects will use the Precision Xtra® ketone meter (K040814 - Abbott Diabetes Care Inc., [name]) to test blood ketones as needed during the study.

D. Phone Device

The phone device that will run the iAPS in this study is a stock Google Pixel 1, 2 or 3/3a Phone, with the iAPS as described in MAF-1625, Amendment #10. The version of Android used in the phone for this study is version 7.1.2, 8.1, 9, 10 or 11. The phone is set to not allow automatic upgrades of the OS. However, if a phone OS upgrade does occur, study staff will not allow subject use of the device and will not release the interlock on the study RM website if the OS version upgrades past the last version that has been tested and verified to support full AID functionality. In that case, the subject's study phone will be replaced.

3.2 Control Algorithm with HMS

A detailed description of the Zone-MPC and HMS control algorithms, meal bolus strategy, and insulin-on-board calculations are provided in Appendix B of the IDE.

The meal bolus strategy used in this study uses full meal boluses for each meal as long as sensor glucose is above 70 mg/dL, as this is necessary for achieving tight glycemic control in pregnancy. The user may adjust the bolus dose up or down at the time of the bolus and needs to approve and confirm the bolus before it is given. This is similar to how boluses are performed in all current insulin pumps, with the dose adjusted, reviewed and confirmed by the user.

The HMS algorithm is also incorporated into the system to provide alerts to the user and clinician of impending hypoglycemia that may require treatment such as fast-acting carbohydrate consumption. Although the HMS algorithm uses the same CGM data as the MPC algorithm, it utilizes a separate algorithm for predicting glucose values. This HMS algorithm was also developed by engineers at Harvard University in collaboration with Sansum Diabetes Research Institute, and the same algorithm was successfully used in G150063, G150122, G160281, G130236, G130147, G180011, G180011/S001, G180011/S002, and G160279/S002. In this study, the HMS will produce an alert on the phone screen when it predicts a glucose value below 65 mg/dL within the next 15 minutes. Treatment will be given at the discretion of the investigator and subject when confirmatory fingerstick glucose is ≥ 63 mg/dL to prevent hypoglycemia as per the subject's usual routine and investigator direction. Treatment with carbohydrates is mandated for hypoglycemia, which is defined as fingerstick glucose < 63 mg/dL and/or symptomatic.

4 STUDY OVERVIEW

4.1 Study Overview

In this study, subjects will use the iAPS for ~48-60 hour period in a supervised outpatient environment. All meals will be bolused for as per usual care. In addition, subjects will perform their usual daily activities (excluding intense exercise) while being accompanied by study medical staff. This includes following a lower carbohydrate diet that women are normally prescribed in pregnancy.

Extension Phase

For subjects who wish to continue use of the system beyond the 48-hour session, they will be trained on use of the study pump and the iAPS during the 48-hour study, and staff will complete the study training checklists. Subjects will then be able to continue with home use of the system all the way through to delivery if they desire, with a 24-hour, 48-hour and 72-hour follow up call, and then at least weekly follow up during the course of the study. The outpatient studies will be closely supervised with easy access for subjects to clinical study teams at each site. High risk obstetrics physician will be available at each site for the clinical research study team.

4.2 Primary Objective

The **primary endpoint** is time within the target glucose range of 63-140 mg/dL overall as assessed by CGM.

4.3 Secondary Endpoints

Secondary safety and efficacy endpoints will include: time within the target range of 63-140 mg/dL overnight, within the range of 63-140 mg/dL postprandial within 2 hours following meals; frequency of hypoglycemia below predefined thresholds of 63 mg/dL and 54 mg/dL, and frequency of hyperglycemia above predefined thresholds of 140, 180 mg/dL and 250 mg/dL. Additional secondary outcomes include markers of hypo- and hyperglycemia, as well as safety events, treatments for hypoglycemia, outside interventions needed, and a failure analysis of the devices/connectivity issues that may occur.

The clinical study will also review any serious adverse events that occur: hypoglycemic events, hyperglycemic events, planned and unplanned outside intervention, other Adverse Events, Serious Adverse Events, Unanticipated Adverse Device Effects, and device complaints for the commercial devices used. A root cause analysis of the event will be performed to determine if it is related to the approved devices - the Continuous Glucose Monitor (CGM) or the Continuous Subcutaneous Insulin Infusion (CSII) pump - the insulin, the AP system, or the control algorithm. Safety of the patient and the fetus will remain the primary goal. The goal of the AP device is to operate without outside intervention apart from HMS alerts suggesting carbohydrate ingestion due to impending hypoglycemia.

5 BACKGROUND INFORMATION

5.1 General Background

This study is being conducted in compliance with the policies described in the study policies document, with the ethical principles that have their origin in the Declaration of Helsinki, with the protocol described herein, and with the standards of Good Clinical Practice.

Informed consent will be obtained before the study procedures are conducted.

Data for this study will be collected on a combination of paper and electronic case report forms, which will be considered the source data. If possible, data will be directly entered into the eCRF as applicable.

A risk-based monitoring approach will be followed, consistent with the FDA “Guidance for Industry Oversight of Clinical Investigations — A Risk-Based Approach to Monitoring” (August 2013).

5.2 Description of Population Studied

The system will be evaluated on up to 21 pregnant adult subjects with type 1 diabetes age 18-45 years old at three clinical sites (Sansum Diabetes Research Institute, Mayo Clinic Rochester MN and Mt Sinai Hospital, New York City). We will recruit pregnant patients between 14-32 weeks gestation. All racial/ethnic groups will be eligible for participation. Subjects will complete a ~48-60 hours closed-loop (CL) session in a supervised outpatient environment with medical staff present, and then have the option to use the CL system at home throughout the remainder of their pregnancy if desired.

6 TRIAL DESIGN

6.1 Overview

This study is a 3-site early feasibility study of pregnancy-specific AP in which we will recruit a total of 21 pregnant women with T1D for a complete 48-60 hours of AP control in a supervised outpatient environment. After completing the 48-hour session, we will offer continued use of the system at home, through as far as delivery if desired, to each subject. Subject data will be reviewed for safety at 24 hours, 48 hours and at 72 hours of home use, and then weekly before being extended a week at a time for the rest of the pregnancy.

6.1.1 Limitations on the Number of Subjects that can be Enrolled

Enrollment will be limited to a maximum of 4 active subjects across all clinical sites at any given time. This will allow for subjects to finish the study before the next is enrolled, and assure available resources for the maximum of 4 possible subjects who may run concurrently.

Enrollment is also limited to only 3 active subjects at a given clinic site at any one time, and each site may only enroll 2 subjects per week maximum.

These limits will remain in place throughout the study.

6.2 Eligibility and Exclusion Criteria

6.2.1 Inclusion Criteria

To be eligible to enroll in this study, subjects must meet all of the following including criteria:

- 1) Age \geq 18 and \leq 45 years at the time of screening.
- 2) Clinical diagnosis of type 1 diabetes
- 3) Currently using an insulin pump at the time of screening.
- 4) HbA1c \leq 9%, as performed by point of care or central laboratory testing. A1c will be assessed at the screening visit.
- 5) Pregnant $14^{0/7}$ to $32^{6/7}$ weeks gestation.
- 6) Singleton pregnancy without any other significant known complications, such as preeclampsia, premature rupture of membranes, 2nd/3rd trimester bleeding, fetal growth or fluid abnormalities.
- 7) No proven or suspected fetal malformations diagnosed in the current pregnancy.
- 8) Bolus for all meals and snacks that contain \geq 5 grams of carbohydrate.
- 9) Willing to switch to Novolog or Humalog, or continue Novolog or Humalog for the duration of closed-loop use.
- 10) Willingness not to start any new non-insulin glucose-lowering agent during the course of the trial.
- 11) Willing to abide by the study protocol and use study-provided devices.
- 12) Have a care partner with the following responsibilities: knowing subject whereabouts and being promptly available for contact by study staff during the day and night, residing in the same dwelling as subject during the night, being agreeable to all device training during the supervised HCL session and additional training on hyper- and hypoglycemia treatment, and assisting with emergency care if needed, such as transportation to the hospital or emergency department.

6.2.2 Exclusion Criteria

Subjects would not be eligible to enroll in this study if they meet any of the following exclusion criteria:

- 1) Known unstable cardiac disease or untreated cardiac disease, as revealed by history or physical examination.
- 2) Concurrent use of AfreZZa or any non-insulin glucose-lowering agent other than metformin (including GLP-1 agonists, Pramlintide, DPP-4 inhibitors, SGLT-2 inhibitors, sulfonylureas).
- 3) Hemophilia or any other bleeding disorder
- 4) Prior history of Preterm Premature Rupture of Membranes (PPROM)

- 5) Significant hyperemesis interfering with carbohydrate intake
- 6) Laboratory results:
 - a. A1C > 9%
 - b. Abnormal liver or renal function (Transaminase >2 times the upper limit of normal, creatinine > 1.5 mg/dL)
 - c. Liver and renal function testing drawn at screening visit or within three months prior to screening (for other purposes) will suffice for enrollment purposes
- 7) Dermatological conditions that would preclude wearing a CGM sensor or infusion site.
- 8) Any condition that could interfere with participating in the trial, based on investigator judgment.
- 9) Participation in another pharmaceutical or device trial at the time of enrollment or during the study.
- 10) Having a direct supervisor at place of employment who is also directly involved in conducting the clinical trial (as a study investigator, coordinator, etc.); or having a first-degree relative who is directly involved in conducting the clinical trial
- 11) History of severe hypoglycemia in the past 6 months
- 12) History of DKA requiring hospitalization in the past 6 months
- 13) Significant chronic kidney disease (eGFR < 60) or hemodialysis
- 14) Significant liver disease
- 15) History of adrenal insufficiency
- 16) History of abnormal TSH consistent with hypothyroidism or hyperthyroidism that is not appropriately treated
- 17) History of high dose steroid use in the past 8 weeks

6.3 Schedule of Events

The trial consists of:

- 1) A screening visit to assess eligibility
- 2) One to two week open-loop data collection while wearing Dexcom G6 CGM
- 3) A 48-60 hour closed-loop session in a supervised outpatient environment with at least one licensed medical provider present at all times
- 4) A follow up phone call 2 hours after discharge from the closed-loop session to assure subject safety and safe transition back to the subject's home insulin pump if they are not continuing in the extension phase.
- 5) Continued use of the system at home, optionally through the end of pregnancy, for subjects who wish to continue use of the system. To achieve this,
 - a. Subjects must consent to training for the extension phase at the time of signing their informed consent form.

- b. Subjects will be trained on use of the study pump and phone while attending the 48-hour study session. Study staff will complete the study pump and phone training checklists, and the site investigator will sign off attestation that the subject is ready to use the study devices at home.
- c. Subjects will have a documented 24-hour, 48-hour and 72-hour check in after taking the system home, requiring the study team to review the remote monitoring system data, and then at least weekly documented contact with each subject. Providers may adjust insulin delivery settings as clinically indicated.
- d. During the first two weeks of home use of the study device, subjects will continue to perform scheduled fingersticks (SMBG) prior to meals, 2 hours after meals, and at bedtime, in addition to fingersticks mandated by the hyperglycemia and hypoglycemia study safety plan. After two weeks, the study glucometer will be downloaded, and if $\geq 90\%$ of CGM values are within 20%/20 mg/dL of SMBG readings, this will be documented in a study contact CRF and the scheduled SMBG requirement for the remainder of that particular participant's time in the study may be removed. However, the participant will still be instructed to perform the confirmatory fingerstick requirements for safety criteria. If a subject's particular data set does not support removing this requirement, that subject will continue to perform scheduled fingersticks per protocol in addition to following the confirmatory fingerstick requirements for safety criteria. This analysis will be repeated for each subject in the study.
- e. Subject's glycemic data will be reviewed and a documented contact will be completed at least weekly after the 72-hour check. If there is a significant deterioration of glycemic control as determined at any time or during the scheduled weekly contacts, leading to a significant worsening time in range compared to baseline (10% or more worsening of time in target range) and time in range consistently below 50%, the site clinical investigator will end the subject's participation in the study (Stopping criteria, section 8.4)
- f. After ~4 weeks, the study Data Safety and Monitoring Board (DSMB) will review a summary of the subject's glycemic data, to include any adverse events, to approve continued use of the system through the remainder of pregnancy if the subject desires. Success criteria based on CGM glycemic metrics, to be presented to the DSMB, before approval can be granted to move beyond three subjects, are the following:
 - a. CGM % Time ≤ 54 mg/dL = 2% or less
 - b. CGM % Time 63-140 mg/dL = greater than or equal to 50%
 - c. No Unanticipated Adverse Device Effects (UADE's)
- g. Follow up visit after delivery: Subjects will be called or seen in person before hospital discharge to ensure they have transitioned safely to their home devices. Maternal and neonatal outcomes will be recorded.

Subjects will be considered enrolled when, after completing the screening visit, the investigator has reviewed all enrollment criteria and signed off on the subject's enrollment. Up to 21 subjects may be enrolled.

In case of illness or cancellation, the visits may be rescheduled at the discretion of the investigator.

Study schedule and interventions are summarized in the table below:

Table . Schedule of Assessments Including Extension

	Screening	Open Loop Data Collection	Hybrid Closed-Loop Phase	End of Study Phone Call (Last study visit)	Extension Phase
Informed Consent	X				
Demographics	X				
Medical History	X				
Diabetes History	X				
Medication Use	X				
Vital Signs ¹	X		X		
Skin inspection (Sensor/Infusion Set Sites)	X				
Fetal Doptones			X		
Laboratory	X				
Point-of-care HbA1c	X				X ⁴
Insulin pump/CGM/glucometer data download	X		X		
CGM Training		X	X		
CGM Placement		X	X		
iAPS & Study Pump Closed-Loop Use			X	X	X
Fingersticks BG as required per protocol ²		X	X	X	X
CGM Calibrations ³		X	X	X	X
Competency assessment prior to discharge home with iAPS			X		
24, 48, and 72 hour contact, then a minimum of weekly contact with subjects.					X

1 – Vital signs at admission, Q12 hours, discharge, and per investigator discretion during the closed-loop phase.

2 – Fingersticks per protocol criteria for hypo and hyperglycemia during closed-loop use.

3 – As required per manufacturer's instructions.

4 – A1c and/or fructosamine may be performed via point-of-care or by central laboratory testing every 4 weeks during the extension phase.

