8.1.2 Reportable Adverse Events

For this protocol, a reportable adverse event includes any untoward medical occurrence that meets one of the following criteria:

1. A serious adverse event
2. An Adverse Device Effect as defined in section 8.1.1, unless excluded from reporting in section 8.2
3. An Adverse Event occurring in association with a study procedure
4. Hypoglycemia meeting the definition of severe hypoglycemia as defined below
5. Diabetic ketoacidosis (DKA) as defined below or in the absence of DKA, a hyperglycemic or ketosis event meeting the criteria defined below

Hypoglycemia and hyperglycemia not meeting the criteria below will not be recorded as adverse events unless associated with an Adverse Device Effect. Skin reactions from sensor placement are only reportable if severe and/or required treatment.

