8.1.5 Coding of Adverse Events

Adverse events will be coded using the MedDRA dictionary. The Medical Monitor will review the investigator's assessment of causality and may agree or disagree. Both the investigator's and Medical Monitor's assessments will be recorded. The Medical Monitor will have the final say in determining the causality.

Adverse events that continue after the participant's discontinuation or completion of the study will be followed until their medical outcome is determined or until no further change in the condition is expected.

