8.1.6 Outcome of Adverse Event

The outcome of each reportable adverse event will be classified by the investigator as follows:

- RECOVERED/RESOLVED – The participant recovered from the AE/SAE without sequelae. Record the AE/SAE stop date.
- RECOVERED/RESOLVED WITH SEQUELAE – The event persisted and had stabilized without change in the event anticipated. Record the AE/SAE stop date.
- FATAL – A fatal outcome is defined as the SAE that resulted in death. Only the event that was the cause of death should be reported as fatal. AEs/SAEs that were ongoing at the time of death; however, were not the cause of death, will be recorded as “resolved” at the time of death.
- NOT RECOVERED/NOT RESOLVED (ONGOING) – An ongoing AE/SAE is defined as the event was ongoing with an undetermined outcome.
 - An ongoing outcome will require follow-up by the site in order to determine the final outcome of the AE/SAE.
 - The outcome of an ongoing event at the time of death that was not the cause of death, will be updated and recorded as “resolved” with the date of death recorded as the stop date.
- UNKNOWN – An unknown outcome is defined as an inability to access the participant or the participant's records to determine the outcome (for example, a participant that was lost to follow-up).

All clinically significant abnormalities of clinical laboratory measurements or adverse events occurring during the study and continuing at study termination should be followed by the participant's physician and evaluated with additional tests (if necessary) until diagnosis of the underlying cause, or resolution. Follow-up information should be recorded on source documents. If any reported adverse events are present when a participant completes the study, or if a participant is withdrawn from the study due to an adverse event, the participant will be contacted for re-evaluation within 2 weeks. If the adverse event has not resolved, additional follow-up will be performed as appropriate. Every effort should be made by the Investigator or delegate to contact the participant until the adverse event has resolved or stabilized.

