8.4 Stopping Criteria

8.4.1 Participant Discontinuation of Study Device

Rules for discontinuing study device use are described below.

- The investigator believes it is unsafe for the participant to continue on the intervention. This could be due to the development of a new medical condition or worsening of an existing condition for the mother or fetus; or participant behavior contrary to the indications for use of the device that imposes on the participant's safety
- Significant deterioration of glycemic control as determined at any time or during the scheduled weekly contacts, leading to a significant worsening time in range compared to baseline (10% or more worsening of time in target range) and time in range consistently below 50%.
- The participant requests that the treatment be stopped
- One distinct episode of DKA related to system function (includes infusion set failure/occlusion leading to DKA)
- One episode of severe hypoglycemia related to system function
- Subject's must discontinue all investigation device (to include study phone and pump) should glucocorticoids be administered to the subject (i.e., Betamethasone for fetal lung maturity).
- Investigation device use (to include study phone and study pump) will be discontinued upon hospital admission for any reason, to include for labor and delivery, and subjects will return to their standard of care or IV insulin drip per hospital protocols and hospital team directed management.

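### Section 6.3 item 5e ends study participation for a deterioration that 8.4.1 treats only as a device stop, so delivery outcomes for those women could go unrecorded

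*Protocol*

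**What the plan says.** Four provisions of the protocol bear on this.

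- **Section 6.3, item 5e.** At the weekly reviews of home use, a woman whose time in range has worsened by 10% or more from baseline and stays below 50% is stopped: "the site clinical investigator will end the subject's participation in the study (Stopping criteria, section 8.4").
- **Section 8.4.1.** The section opens "Rules for discontinuing study device use are described below". One of its rules is the same deterioration criterion, in nearly the same words: "10% or more worsening of time in target range) and time in range consistently below 50" per cent. Another is that device use "will be discontinued upon hospital admission for any reason, to include for labor and delivery".
- **Section 6.3, item 5g.** After delivery, and before hospital discharge, women are called or seen to confirm that they are safely back on their own devices. The item then adds: "Maternal and neonatal outcomes will be recorded".
- **Section 8.4.2.** Enrollment stops and all device use is discontinued once two subjects have met the deterioration criterion.

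**The concern.** One trigger has two different consequences, and the cross-reference in 5e leads to the one that 5e does not state. A site following 8.4.1 would take the woman off the system and could keep her in the study. A site following 5e literally would close her participation, and might then have no reason to contact her at delivery.

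Item 5g is the only place where the protocol asks for maternal and neonatal outcomes. The women concerned are those whose glucose control became worse on the investigational system. Section 7.3.1.5 names large or macrosomic babies, polyhydramnios and neonatal hypoglycemia as risks of chronic hyperglycemia, and section 4.3 puts the safety of mother and fetus first. If outcomes were missing for exactly these women, the summary of pregnancy outcomes would look better than it should.

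**Working it through.** This is mainly a check of text. The arithmetic only sizes it.

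1. **Same criterion, different act.** Item 5e cites section 8.4 as a whole. Section 8.4.1 holds its only participant-level rules, and 8.4.2 concerns the study overall. The criterion in 5e matches the one in 8.4.1. The act is the end of participation in 5e and the end of device use in 8.4.1.

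2. **A device stop is compatible with staying in the study.** Section 8.4.1 stops the device on admission for labor and delivery, yet 5g requires contact after that and before discharge. So at least one stop under 8.4.1 leaves the woman in follow-up.

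3. **Reach of 5g.** It refers to subjects without excluding those stopped early. But it belongs to item 5, which is about women who continue home use, and its stated purpose is the return to home devices around delivery. A woman stopped weeks before has already made that change. Whether 5g reaches her is unclear, and this is so for every stop before delivery under 8.4.1 (glucocorticoids, ketoacidosis, severe hypoglycemia, her own request), not only for deterioration.

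4. **Whether another provision would capture the outcomes.**
   - Section 8.1.2: "Hypoglycemia and hyperglycemia not meeting the criteria below will not be recorded as adverse events unless associated with an Adverse Device Effect". Deterioration alone therefore need not open an adverse-event record.
   - Section 8.1.5: adverse events that continue after a participant's "discontinuation or completion of the study will be followed until their medical outcome is determined" or no further change is expected. This follows an existing event and does not ask for delivery outcomes.
   - Section 8.1.6: "if a participant is withdrawn from the study due to an adverse event, the participant will be contacted for re-evaluation within 2 weeks". This applies only where an adverse event was the reason for withdrawal.
   - Section 9.4 concerns voluntary withdrawal and the use of data up to that time. It does not restore 5g for a woman stopped by the investigator.

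5. **How many women.** Section 8.4.2 halts all device use at two. With the planned 21 subjects, 2/21 = 9.5%. The extension is optional, so the denominator may be smaller: if 10 women entered it (an assumed number), 2/10 = 20%. A third woman could be added only if she met the criterion before use was halted; section 6.1.1 caps active subjects at four.

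6. **Whether the 2-week re-contact would reach delivery.** Weeks from stop to delivery = delivery week − week of the closed-loop session − weeks of home use. Section 2.3 gives a mean gestation of 22.2 weeks for the first eight participants. Delivery at 34 to 39 weeks and a stop after 1 to 8 weeks of home use are assumptions.
   - Longest: 39 − 22.2 − 1 = 15.8 weeks.
   - Middle: 37 − 22.2 − 4 = 10.8 weeks.
   - Shortest: 34 − 22.2 − 8 = 3.8 weeks.
   - Entry at the upper limit of 32 6/7 (32.86) weeks with a stop after 1 week: 34 − 32.86 − 1 = 0.1 to 39 − 32.86 − 1 = 5.1 weeks.

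   For entry at the mean gestation, a re-contact within 2 weeks falls before delivery throughout this range. Only for late entry might the two coincide.

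**The case against.** The best defense is that the two texts can be reconciled. The extension consists of using the system at home, so ending participation in it and stopping the device come close to being one act, and 5e names 8.4 as its authority. Women who decline the extension finish with a phone call 2 hours after discharge, and the schedule table calls the end-of-study call the last study visit. The protocol therefore does not promise delivery outcomes for every woman off the system. On this view any gap lies in the scope of 5g, not in a conflict between 5e and 8.4.1.

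Part of this stands. The scope of 5g is indeed unclear, and rewording 5e alone would not settle it. That makes the gap wider, since it takes in every early stop, and means that both items need amending. It does not remove the mismatch: 5e speaks of participation in the study, not in the extension.

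A reader might infer more than the text supports in three ways.

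- That the protocol ends follow-up for these women. It does not say so. Item 5g excludes nobody, and a site that treats 5e as a device stop would still record outcomes.
- That stopping under 8.4.1 can never mean leaving the study. The labor rule shows this for one trigger only, and the list mixes triggers of different kinds.
- That nothing at all would be captured. Deterioration judged to be associated with an adverse device effect is reportable, and section 8.1.1 counts fetal death and congenital anomaly as serious adverse events, so a site still in touch with the woman would report them.

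**Conclusion.** The mismatch between 5e and 8.4.1 is certain from the text. The loss of outcomes is a possible result of following 5e literally, not something the protocol states. The point is minor: about two women at most under this criterion (9.5% of 21, or 20% of an assumed 10 in the extension), and maternal and neonatal outcomes are neither the primary endpoint nor among those listed in section 4.3. It still deserves correcting, because any loss would fall on women whose glucose control worsened on the system. Stops for other 8.4.1 reasons share the uncertainty over 5g. The limit of two does not apply to them, and the protocol gives no rate from which to estimate their number. The weeks between stop and delivery rest on the assumed timing of both; the text finding does not depend on them.

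**What to change.** Make two edits in section 6.3.

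- **Item 5e:** replace the end of study participation with discontinuation of study device use under section 8.4.1, and add that follow-up continues through delivery unless the woman withdraws consent.
- **Item 5g:** state that maternal and neonatal outcomes are recorded for every woman who entered the extension, including those stopped early for any reason in 8.4.1.

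The cost is one call or chart review at delivery for each woman stopped early. The stopping criterion, the endpoints and the sample size stay as they are.
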